15 STATISTICAL METHODS AND CONSIDERATIONS

Prior to the analysis of the final study data, a detailed Statistical Analysis Plan (SAP) will be written describing all analyses that will be performed. The SAP will contain any modifications to the analysis plan described below.

15.1 Data Sets Analyzed

Analyses will follow a modified intent to treat (mITT) paradigm. All eligible participants who are randomized into the study and receive at least one dose of the study drug will be included in the analysis.

Based on interim analysis for futility, it was decided to halt recruitment beginning January 19th, 2021. The final data analysis will begin:

- after all 30-day post drug follow-up has been completed for all randomized patients,
- after chart review and data cleaning are complete, and
- after approval of the SAP by the study team.

15.2 Demographic and Baseline Characteristics

The following demographic variables at enrollment will be recorded: race, ethnicity, sex, date of birth, height and weight.

15.3 Analysis of Primary Endpoints

Due to changes in standard of care, the initial D-dimer endpoint may no longer be clinically meaningful. Standard care of treatment for COVID-19 has changed to include anti-inflammatory

steroids which decrease D-dimer levels. Looking for an impact of dipyridamole to further reduce already diminished D-dimer levels is of limited value. In light of the changes to standard of care, it was decided to evaluate the effect of dipyridamole on clinical outcomes more directly by elevating the hierarchical composite outcome from a secondary endpoint to a primary endpoint.

The first primary endpoint is the relative change in D-dimer level over time during up to 14 days of hospitalization. We will assess the trend across D-dimer measurements obtained every second day, but we anticipate that some patients will have fewer measures (e.g. due to discharge before day 14). Linear mixed effects regression will be used to assess the longitudinal trend in log-transformed D-dimer values. The regression model will have a fixed intercept and fixed slope for each treatment arm, and a random intercept and random slope for each subject. The model will also include treatment interactions by stratification factor (sex and age). The primary hypothesis is that the treatment arm will have a smaller fixed slope than the control arm, indicating that treated subjects' D-dimer levels either increase more slowly or decrease relative to those of the control subjects.

Mixed effects regression makes use of all available information for each subject -- even a subject with a single D-dimer measurement can be included. This technique efficiently makes use of the partial or full data observed from each subject, implicitly weighting subjects more if they have more observed points. We note that subjects who do well and are discharged relatively earlier will be somewhat down-weighted due to having fewer measurements, but this is appropriate since our primary aim is to assess moderation of D-dimer increase in-hospital. Discharge and other outcomes are discussed below as secondary aims. We also note that this approach quantifies the change in D-dimer as a linear trend on the log scale. Our preliminary analysis of D-dimer levels in patients with COVID-19 supports this simple approach to quantifying D-dimer variation. Although D-dimer can fluctuate from day-to-day, the longer-term trend is primarily linear, but we acknowledge that some patients may exhibit other patterns of change.

The second primary endpoint is a hierarchical composite of:

- Time of death from any cause during study duration
- Number of days on mechanical ventilation during study hospitalization
- Decrease in SpO₂/FiO₂ ratio of at least 50 units relative to baseline at any time during the observation period, and
- The cumulative sum of COVID ordinal scores during study hospitalization.

The composite endpoint will be nonparametrically assessed by comparing global composite rank score outcomes²⁴ across pairs of patients and evaluating a 'win ratio' using the Mann-Whitney U statistic. Each pair consisting of one treated and one untreated subject is ranked as defined below:

1. If both subjects die, then the subject who lives longer wins.
2. If exactly one subject dies, then the subject who does not die wins.
3. If the subjects are tied after step 2 (neither subject dies), then the subject with fewer days on ventilator wins.
4. If the subjects are tied after step 3, and only one of the subjects has a decrease in SpO₂ of 50 or greater, then the subject who does not have the decrease in SpO₂ wins.

5. If the subjects are tied after step 4, then the subject with lower Ordinal score wins.
6. If the subjects are tied after step 5, then their final result is a tie

The win proportion is the probability that a treatment patient experiences better outcomes when compared to a placebo patient, thus representing the effect size. The analysis is powered to a 0.67 win proportion. For the efficacy endpoint using the O'Brien-Fleming method to correct for interim analyses, we will use a P value cutoff of 0.006 for the midway point analysis and 0.044 for the final analysis, yielding an overall alpha (type I error rate) of 0.05.

15.3.1 *Interim Analyses of Primary Endpoints*

When approximately 25% and 50% of participants have completed the study or 10 deaths have occurred (whichever occurs first), an interim analysis for safety and futility will be conducted by the DSMB. The interim analyses for efficacy will be limited to the review after 50% of participants have completed the study to limit the cost to power from multiple interim analyses.

The interim analysis of benefit for the primary endpoint will be conducted on a binary version of patient-level D-dimer change rates. Rates will be estimated separately for each patient by simple linear regression and dichotomized by whether the rates was above a 5% daily increase.

Treatment groups will be compared by a Fisher's exact test. We will use the O'Brien-Fleming method and Lan-DeMets alpha spending functions to preserve an overall Type I error rate of 0.05. Thus, the interim analysis will use a significance threshold of $\alpha = 0.006$ (based on 45 patients), and the remaining 0.044 of alpha will be divided evenly between the final analyses of the two primary endpoints.

For futility of the D-dimer endpoint, if the lower limit for the 95% confidence interval of the daily change in D-dimer is above 9% *for the dipyridamole population* at the time of the 50% interim analysis, the trial will be stopped.

It was decided in the December 2020 DSMB meeting to conduct benefit and futility analyses of the composite hierarchical primary endpoint for all patients with study completion as of December 31, 2020. We proceed with the win ratio analysis described above but base futility and benefit decisions on the conditional power approach described in Lan and Trost (1999) and advanced in Siu and Lan (2001) and Lachin (2006). This approach calculates the condition power (CP), defined as the probability of finding a significant result at the end of the study given the interim results and a presumption that the data reflect the true effect size. Decision thresholds are predetermined as:

- $CP \geq 0.9$: Stop study for benefit
- $0.8 \leq CP < 0.9$: Continue study to planned $N = 127$
- $0.3 \leq CP < 0.8$: Continue study to with re-estimated sample size not to exceed 160
- $CP < 0.3$: Stop study for futility

15.4 *Analysis of Secondary Endpoints*

We will conduct secondary analyses on each component of the hierarchical composite endpoint:

- Time to death
 - *Analysis:* Cox proportional hazards regression
- Number of days on mechanical ventilation during study hospitalization
 - *Analysis:* Poisson regression with subject-level random effects
- Dichotomized (yes/no) decrease in $\text{SpO}_2/\text{FiO}_2$ ratio of at least 50 units relative to baseline at any time during the observation period
 - *Analysis:* Logistic regression
- Cumulative sum of COVID ordinal scores during study hospitalization
 - *Analysis:* Mann-Whitney U-test (nonparametric)

We will analyze an additional secondary endpoint:

- Days free of organ support, where organ support is defined as receipt of invasive or non-invasive mechanical ventilation, high flow nasal oxygen, vasopressor therapy, ECMO support, or COVID-related dialysis, and
- Death at any time is assigned a value of 0 days.
 - *Analysis:* Mann-Whitney U-Test (nonparametric)

Each analysis will include interactions of the study drug by stratification factor.

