7.2 Win Ratio Calculations

The standard of care treatment for COVID-19 changed with the introduction of anti-inflammatory steroids, which appear to influence D-dimer concentrations. It was therefore determined to elevate the secondary endpoint to become a co-primary endpoint. This endpoint is a composite of clinical outcomes including death, survival time, mechanical ventilation days, decrease in SpO₂/FiO₂ ratio, and cumulative COVID-19 ordinal scores.

This endpoint will be assessed nonparametrically by comparing outcomes across all possible pairs of treatment-placebo patients and evaluating a 'win ratio' using the Mann-Whitney U-statistic (Pocock et al., 2012). See Section 8.6.2.2 for details. The win proportion is interpreted as the probability that a study drug patient experiences a better outcome than a placebo patient, and in this sense, it represents the effect size for the analysis. We powered our analysis on a presumed 0.67 win proportion (i.e. a patient on study drug is twice as likely to have a better outcome as a patient on placebo). We calculated sample size requirements using the formulas provided in Yosef et al. (2019).

Because we set a 0.006 Type I error significance (alpha) for the interim analysis for benefit of D-dimer, we could only use 0.044 of the original 0.05 for the primary endpoints. We divided the 0.044 between the two co-primary endpoints, leaving a 0.022 two-sided Type I error. Accounting for a 10% dropout, we require 127 patients to have 80% power to significantly detect a win ratio of 0.67.

8 General Analysis Considerations

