9.6 Treatment Compliance

We will summarize participant medication exposure, including missed doses, using descriptive statistics including n, mean, median, standard deviation, minimum, and maximum. The summary will include the total number of patients on drug from Day 1 through Day 14 separately by treatment.

10 Efficacy Analyses

Continuous variables will be summarized using descriptive statistics including n, mean, median,

standard deviation, minimum, and maximum. Qualitative variables will be summarized using counts and percentages. Summaries will be provided by treatment groups and overall. Two-sided hypotheses will be tested for efficacy endpoints at the 5% level.

Unless otherwise stated, analyses will be performed on the mITT population and will be programmed in SAS software (SAS Institute, Inc., Cary, NC), while graphics will be generated using R (R Core Team, 2020).

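### The final significance level for each primary endpoint is given as 0.044, 5% and 0.022 in different places, and the interim alpha figures also disagree

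*Protocol*

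**What the plan says.** **Final level**

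- Protocol 15.3, after describing the composite and its win proportion: "we will use a P value cutoff of 0.006 for the midway point analysis and 0.044 for the final analysis". The sentence goes on to give an overall alpha of 0.05 and does not mention a split between two endpoints.
- Protocol 15.3.1: "the remaining 0.044 of alpha will be divided evenly between the final analyses of the two primary endpoints", which is 0.022 each.
- SAP 7.2: "We divided the 0.044 between the two co-primary endpoints, leaving a 0.022 two-sided Type I error". The sample size rests on this level: with 10% dropout, "we require 127 patients to have 80% power to significantly detect a win ratio of 0.67".
- SAP 10.1 (D-dimer) and SAP 10.2 (composite): 0.022 for each primary.
- SAP section 10, opening text: "Two-sided hypotheses will be tested for efficacy endpoints at the 5% level". No exception is stated, although SAP 8.7 applies a Bonferroni adjustment to the five secondary analyses.

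**Interim level for the D-dimer benefit test**

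- SAP 8.6.2.1: 0.003, as a projection for 40 patients.
- Protocol 15.3.1 and SAP 10.1: 0.006, based on 45 patients.
- SAP 10.2: 0.006, based on 40 patients.

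**Conditional power**

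Protocol 15.3.1 records a decision "to conduct benefit and futility analyses of the composite hierarchical primary endpoint", and at a conditional power of 0.9 or more the rule is "Stop study for benefit". The Protocol Synopsis (Planned Interim Analyses) and SAP 8.6.2.2 both say this approach needs no Type I error adjustment. SAP 8.6.2.2 also says that the interval for the win ratio spends only the alpha left over from the D-dimer analysis.

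**The concern.** The same two tests carry three thresholds. A primary p-value between 0.022 and 0.044 is significant under the 0.044 and 5% lines but not under 0.022. One between 0.044 and 0.05 is significant under the 5% line only. Recruitment had been halted, but Protocol 15.1 and SAP 8.1 show the final analysis still to come. The threshold therefore has to be fixed beyond argument before the result is seen.

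The interim figures matter because 0.044, and hence 0.022, is what remains after 0.006 is taken from 0.05. If the interim alpha or the count behind it is in doubt, the origin of the final level is in doubt too.

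The no-adjustment claim is sound for stopping for futility, which cannot add false positives. It is not supported for a rule that can also stop for benefit.

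**Working it through.** **1. Which final level does the design rest on?**

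Inputs from SAP 7.2: win proportion 0.67, 80% power, 10% dropout, two-sided alpha 0.022. Allocation is 1:1 (SAP 6.1). The SAP takes its formula from a cited paper that is not available here, so I used the Noether formula for the Mann-Whitney test:

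N = (z(1−α/2) + z(0.80))² / (12 × 0.25 × (0.67 − 0.5)²) = (z(1−α/2) + z(0.80))² / (3 × 0.17²), rounded up and then divided by 0.9.

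Family-wise upper bound if the level is applied to each primary: 0.006 + 2α.

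| α per primary | Evaluable N | With 10% dropout | Family-wise bound |
|---|---|---|---|
| 0.022 | 113.1 → 114 | 126.7 → 127 | 0.050 |
| 0.044 | 94.1 → 95 | 105.6 → 106 | 0.094 |
| 0.05 | 90.5 → 91 | 101.1 → 102 | 0.106 |

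The plan's 127 is reproduced exactly at 0.022 and at neither other level. If the three tests were independent, the last two bounds would be 0.092 and 0.103.

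**2. How wide is the disputed zone?**

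Assume all 100 enrolled patients are analysed 1:1, unstratified and without ties. The smallest significant win proportion is then 0.5 + z(1−α/2)/√(3 × 100): 0.632 at 0.022, 0.616 at 0.044 and 0.613 at 5%. An observed value of 0.613 to 0.632 passes at 5% and fails at 0.022. This is indicative only, because the planned analysis is stratified.

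**3. Do the interim figures fit one rule?**

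Lan-DeMets spending of O'Brien-Fleming type, with t = interim n / total n:

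- Two one-sided 0.025 functions: 4 × [1 − Φ(2.241/√t)].
- One two-sided 0.05 function: 2 × [1 − Φ(1.960/√t)].

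| n / total | Two one-sided 0.025 | One two-sided 0.05 |
|---|---|---|
| 40/80 | 0.0031 | 0.0056 |
| 45/80 | 0.0056 | 0.0090 |
| 40/127 | 0.0001 | 0.0005 |
| 45/127 | 0.0003 | 0.0010 |
| 40/160 | 0.00001 | 0.0001 |
| 45/160 | 0.00005 | 0.0002 |

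With a total of 80, the first rule gives both 0.003 at 40 and 0.006 at 45. The second gives 0.006 at 40 but neither of the other two figures. No single rule gives both 0.003 and 0.006 at 40. With a total of 127 or 160, neither rule gives more than 0.001, so the total behind the figures has to be stated as well.

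**4. The conditional-power benefit stop**

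I assumed the current trend, t = n/127, and one-sided 0.011 at the end (z = 2.290):

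- Conditional power of 0.9 is reached at Z = √t × (2.290 + 1.282√(1−t)).
- Conditional power of 0.3 is reached at Z = √t × (2.290 − 0.524√(1−t)).

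The composite's null error came from numerical integration. The family-wise bound adds 0.006 + 0.022 for D-dimer, and 0.011 for the composite's lower tail if futility is non-binding. The interim count for the composite is not stated, so a range is shown.

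| Assumed interim n | 45 | 50 | 55 | 64 | 80 | 100 |
|---|---|---|---|---|---|---|
| Binding futility, stop counts as rejection | 0.056 | 0.052 | 0.049 | 0.045 | 0.041 | 0.039 |
| Binding futility, 0.022 critical value also needed | 0.043 | 0.044 | 0.044 | 0.044 | 0.041 | 0.039 |

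The first row crosses 0.05 at about 53 patients. With non-binding futility the bound runs from 0.071 down to 0.052 if a stop alone counts, and from about 0.058 to 0.052 if the critical value is also required. Allowing re-estimation up to 160 changes these bounds by at most 0.0006.

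**The case against.** The strongest reply is that the intended level can be recovered from the text.

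- **0.044.** The sentence in Protocol 15.3 speaks of a single efficacy endpoint and gives an overall 0.05, which 0.006 + 0.044 already reaches. Protocol 15.3.1 then splits the 0.044. So 0.044 can be read as the combined level, and 0.094 as a worst case that the same section rules out. Protocol section 15 also says "The SAP will contain any modifications to the analysis plan described below", which lets the SAP's 0.022 govern. This largely stands. What remains is that a cutoff for a p-value is naturally applied to one test, and the sentence follows the composite's own text.
- **5%.** This line is a general preamble, and the specific levels in SAP 10.1 and 10.2 would normally prevail. That is the likely intent. But the line is in the SAP, so the SAP's precedence over the protocol does not resolve it. It also conflicts with the Bonferroni rule for the secondaries.
- **Interim figures.** 0.003 at 40 and 0.006 at 45 agree under one rule with a total of 80, so the first may simply be a projection. That is right as far as it goes. The 40 in SAP 10.2 still conflicts with 0.003 at 40 in SAP 8.6.2.1 and with 45 in SAP 10.1 and Protocol 15.3.1.
- **Conditional power.** No benefit stop occurred, the interim count is assumed, and with binding futility the bound exceeds 0.05 only for an early look at which the stop alone counts as rejection. All true, so this part is a correction of wording only.

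**Conclusion.** The conflict is real. The weight of the text and the arithmetic both favour two-sided 0.022 for each primary, but the 0.044 cutoff and the unqualified 5% line remain in the current documents. Read literally for each primary, they allow family-wise error of up to 0.094 and 0.106 against an intended 0.05. These are upper bounds by simple addition. The reproduction of 127 uses the Noether formula in place of the SAP's cited one.

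For the interim alpha, only the mismatch is shown. The documents do not reveal which count or which spending rule is wrong.

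The no-adjustment statement is too broad because it covers a benefit stop. Enrollment was halted at 100 for futility, so this has no consequence for the result.

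**What to change.** 1. In Protocol 15.3 and the opening of SAP section 10, state two-sided 0.022 for each primary endpoint. Label 0.044 as the combined final level for both.
2. Limit the 5% line so that it excludes the primaries and the five Bonferroni-adjusted secondaries (0.05/5 = 0.01 each, SAP 8.7).
3. Reconcile SAP 8.6.2.1, 10.1 and 10.2 with Protocol 15.3.1 by stating the actual D-dimer interim count, the total it is divided by and the spending rule. If 0.003 was only a projection for 40 patients, say so.
4. In the Protocol Synopsis and SAP 8.6.2.2, limit the no-adjustment statement to futility. Report the composite's interim count, and state that benefit and futility were both assessed, that no benefit stop occurred and that no efficacy claim rests on that look.

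The cost is wording in the two documents. Data, sample size and models do not change. The one consequence is that a primary p-value between 0.022 and 0.05 can no longer be called significant.

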15.5 Analysis of Exploratory Endpoints

The DICER study contains four major kinds of exploratory endpoints (listed in Section 3.5): continuous, change over time (continuous), binary, and time to event. All analyses will be based on the mITT population except where specified in the definition of the endpoint.

We will analyze continuous endpoints by ANOVA with treatment and stratification factors (sex and age) as predictors.

We will analyze continuous change over time endpoints by mixed linear effect models using the same methodology described in Section 10.1 for the D-dimer primary efficacy endpoint.

We will analyze binary endpoints by logistic regression with treatment and stratification factors (sex and age) as predictors.

We will analyze time-to-event by Cox proportional hazards regression with treatment and stratification factors (sex and age) as predictors.

In all analyses, the only estimate of interest will be the difference between treatment arms. We will include treatment interactions by stratification factor in all models, and we will fit separate models where age is continuous versus where age is represented by an indicator variable for age ≥ 65 years. Hypothesis tests will be two-sided.

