SECONDARY OUTCOMES	Days alive and free of organ support, where organ support is defined as receipt of invasive mechanical ventilation, vasopressor therapy, ECMO support, or dialysis. Individual components of composite endpoint.
EXPLORATORY OUTCOMES	Time to improvement in oxygenation status, initiation of mechanical ventilation or ICU care, proportion of patients requiring mechanical ventilation, change from baseline in hematology labs (C-reactive protein, LDH, ferritin, leukocyte count, platelet count) among patients with abnormal baseline values, time to hospital discharge, incidence of hospital readmission, proportion of surviving patients requiring supplemental oxygen at discharge, number of days on supplemental oxygen, arterial or venous thromboembolism (separately and pooled), gene expression / function / activation of peripheral blood leukocytes, and decrease in each of the following among patients with elevated baseline values: glomerular filtration rate, neutrophil activation, inflammatory / anti-inflammatory / other cytokines, and coagulant and anti-coagulant cytokines.
NUMBER OF PARTICIPANTS	The original protocol called for the enrollment of 80 participants in order to complete the study, randomized 1:1 to dipyridamole or placebo. However, the standard of care changed with the introduction of anti-inflammatory steroids which suggested an increase in sample size may be necessary, thus it was decided to double the number of participants to 160. During the January DSMB meeting it was decided to halt enrollment at 100 participants due to futility.
PARTICIPANT SELECTION CRITERIA	
Inclusion Criteria:
 
 1. Age \geq 18 years 2. Willing and able to provide informed consent prior to performing study procedures unless they have a legally authorized representative (LAR) 3. Confirmed coronavirus (SARS-CoV-2) infection 4. Currently hospitalized or anticipated hospitalization requiring supplemental oxygen 
Exclusion Criteria:
 
 1. In the opinion of at least two physicians, unlikely to survive for >48 hours from screening 2. Concurrent enrollment in a clinical trial with a cytokine inhibitor (targeting IL-6, IL-6R, IL-1, or Janus kinase). Use of remdesivir is permitted.

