15.7 Sample Size and Randomization

We will enroll 100 participants to complete this study based on the power calculation. Patients will be recruited for this study and randomized in a 1:1 ratio using stratified random blocks. This study is a proof-of-concept multi center, single-blinded, randomized, controlled trial to evaluate the effectiveness of dipyridamole to reduce progressive coagulation dysfunction associated with coronavirus infection.

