5.2.4 Exploratory Endpoints

Based on consultation with the DICER researchers, SABER will only analyse a subset of the exploratory endpoints specified in the original protocol. Numbers in the following list (e.g. #17) refer to Section 3.4 Exploratory Outcomes in the protocol, version 5.0.

6. Blood Oxygenation
 - Time to increase in daily average SpO₂/FiO₂ ratio of at least 50 units relative to Day 1 during the observation period (#17)
7. Ventilation
 - Initiation of mechanical ventilation or ICU care during observation period (yes/no) (#6)
 - Initiation of mechanical ventilation during observation period (yes/no) (#11)
 - Initiation of ICU care during observation period (yes/no)
8. Change from baseline at Day 5 for: C-reactive protein, LDH, ferritin, total leukocyte count, neutrophils, lymphocytes, and platelet count in the blood (#4)
 - Daily changes from Day 1 in neutrophils and lymphocytes
9. Hospitalization
 - Time to hospital discharge (#7)

- Incidence of hospital readmission during study duration (#30)
- 10. Supplemental Oxygen
 - Proportion of surviving patients still requiring supplemental oxygen at the end of the observation period (#8)
 - Number of days on supplemental oxygen during observation period (#9)
- 11. Imaging: Proportion of study population with each of the following:
 - Arterial or venous thromboembolism diagnosed by imaging study during study duration (#25)
 - Venous thrombosis diagnosed by imaging study during study duration (#26)
 - Arterial thrombosis diagnosed by imaging study during study duration (#27)
- 12. Change from Day 1 in daily average glomerular filtration rate (GFR) during observation period, assessed daily through Day 5 (#28)
- 13. An alternative version of the second co-primary endpoint decision-rule:
 - Time to death from any cause during study duration
 - Number of days on mechanical ventilation during study hospitalization
 - A dichotomized (yes/no) decrease in daily average $\text{SpO}_2/\text{FiO}_2$ ratio of at least 50 units relative to enrollment date at any time during the observation period
 - A dichotomized (yes/no) increase in Ordinal Score at any time relative to enrollment
 - Analyze dichotomized (yes/no) increase in Ordinal Score at any time relative to enrollment as a standalone endpoint

Additional analyses done separately from SABER (to be done at a future date):

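### For binary exploratory endpoints, the logistic model with treatment interactions does not estimate the arm difference the plan asks for, and with few events it usually has no finite fit

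*Protocol*

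**What the plan says.** Protocol 15.5 sets one rule for every yes/no exploratory endpoint: "We will analyze binary endpoints by logistic regression with treatment and stratification factors (sex and age) as predictors". It then adds: "We will include treatment interactions by stratification factor in all models". Two versions are to be fitted, one with age continuous and one with an indicator for age 65 or over. The stated target is narrow: "the only estimate of interest will be the difference between treatment arms". SAP 10.4 repeats all of this.

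The endpoints covered by the rule include arterial, venous and pooled thromboembolism (SAP 5.2.4, item 11).

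On sample size, the Protocol synopsis records: "During the January DSMB meeting it was decided to halt enrollment at 100 participants due to futility". Protocol 15.7 says patients are "randomized in a 1:1 ratio using stratified random blocks", so there are about 50 per arm.

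The opening text of SAP section 10 says: "Two-sided hypotheses will be tested for efficacy endpoints at the 5% level". For the logistic models, neither document names the test (Wald, likelihood-ratio or exact), the coding of the factors, a minimum number of events, or what to do with an empty cell.

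**The concern.** The model and the target do not match. Once treatment interacts with sex and age, no single coefficient is the overall arm difference, and the plan does not say how the stratum effects are to be combined into one.

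The model is also too large for sparse outcomes. If an arm has no events, or one sex or age group within an arm has none, at least one coefficient has no finite estimate. Software then prints a very large coefficient and standard error, and any result built on them is uninformative.

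Thrombosis is the clinical outcome closest to the drug's rationale in Protocol sections 1 and 2. It is also where low counts are most plausible, above all for arterial events.

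**Working it through.** The documents give no expected rate, power or event count for these endpoints, so there is no planned figure to reproduce.

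**Inputs.** From the documents: N = 100, 1:1, the model above. Assumed, because the documents give no figures: event rate 2% to 40%, equal in both arms; 50% to 60% male; 35% to 50% aged 65 or over.

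**Step 1: what the treatment coefficient means.** With T = treatment, S = sex, A = age group:

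logit(p) = b0 + b1·T + b2·S + b3·A + b4·T·S + b5·T·A (six parameters)

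The treatment log odds ratio in stratum (S, A) is b1 + b4·S + b5·A. Under reference coding b1 is the effect at S = 0, A = 0 only. This is so at any event rate.

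**Step 2: when no finite solution exists.** Because treatment interacts with both covariates, the model is two separate three-parameter models (intercept, sex, age), one per arm of about 50.
- An arm with 0 events has an intercept that goes to minus infinity.
- An arm with 1 event has that event in one sex, so the other sex has none and the sex coefficient diverges.

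So 0 or 1 event in either arm always rules out a finite fit. That alone gives a floor that can be computed by hand. With P = (1−r)^50 + 50·r·(1−r)^49, the floor is 1 − (1−P)²:
- r = 2%: P = 0.364 + 0.372 = 0.736; floor = 1 − 0.264² = 93%
- r = 4%: P = 0.130 + 0.271 = 0.401; floor = 1 − 0.599² = 64%
- r = 8%: P = 0.0155 + 0.0672 = 0.083; floor = 1 − 0.917² = 16%

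**Step 3: full frequency of non-finite fits.** Each simulated trial was tested for separation by linear programming. The table covers the age-indicator model; ranges reflect the assumed sex and age mixes.

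| Event rate | With interactions | Without interactions |
|---|---|---|
| 2% | 99% | 76–81% |
| 4% | 91–94% | 42–51% |
| 8% | 59–67% | 9–13% |
| 12% | 28–35% | about 2% |
| 20% | 4–9% | 0% |
| 40% | 0% | 0% |

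At 10% the interaction model fails in 43–51% of trials, so it usually fails only below roughly 8–10%. The continuous-age version fails less often: 28% at a 10% rate.

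**Step 4: fixed splits of 50 v 50.** Median Wald p for the treatment coefficient:

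| Events | With interactions | Sex and age, no interactions |
|---|---|---|
| 5 v 1 | 0.98 | 0.13 |
| 6 v 1 | 0.98 | 0.08 |
| 8 v 2 | 0.67 | 0.06 |
| 6 v 0 | 1.0 | 1.0 |

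With the interactions, 5 v 1 and 6 v 1 gave no finite fit in any dataset (100%), and 8 v 2 in 77–80%.

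**Step 5: 6 v 0 under other tests.** Fisher's exact p = 0.027. Median values for the rest:
- Likelihood-ratio without interactions (1 df): 0.003
- Likelihood-ratio on all three treatment terms of the six-parameter model (3 df): 0.033
- Likelihood-ratio on its treatment coefficient alone (1 df): 0.12–0.16
- Firth with sex and age, no interactions: 0.011
- Firth on the treatment coefficient of the six-parameter model: 0.23

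**The case against.** Several points on the other side stand.

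- **A reader might infer that a 6 v 0 split would be reported with p near 1 because of the interactions.** The documents do not support this. The plan does not call for a Wald test: it says "analyses will be performed on the mITT population and will be programmed in SAS software" and names no test for these models. A likelihood-ratio test gives 0.003 or 0.033, depending on the model. The Wald failure at 6 v 0 comes from the empty arm and occurs with treatment alone. The harm from the interactions shows in splits such as 5 v 1. Even so, the likelihood-ratio test is only a partial rescue: 0.003 belongs to a model the plan does not specify, and 0.033 tests three terms jointly, not an arm difference.
- **A reader might infer that the venous thrombosis analysis will usually fail.** That is unproven. The only figure in the documents is the background statement in Protocol section 1 of up to 40%, and at 40% the problem disappears. That figure is an upper bound, not a forecast for this trial.
- **Any infinite coefficient is not the same as an infinite treatment coefficient.** At an 8% rate, 62% of simulated trials separated, but the treatment coefficient diverged in 31% with younger women as reference. With the older group as reference the figures were 65% and 55%. The plan does not fix the coding, and an effect averaged over strata would diverge more often than that of a single stratum.
- **The data would not be lost.** SAP section 10 plans counts and percentages by arm, so a lopsided split would be visible. SAP 8.7 requires confirmation of exploratory findings before they are reported.

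**Conclusion.** The point holds in two parts. First, at any event rate and under reference coding, the specified model's treatment coefficient is a one-stratum effect and not the arm difference that the plan calls its only target. Second, with few events (an assumed rate below about 8–10%, or 0 or 1 event in either arm whatever the rate) the age-indicator model usually or always lacks a finite solution, and the plan has no fallback.

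The second part rests on assumed event rates and sex and age mixes. It is plausible for arterial thrombosis and open for venous thrombosis. It does not show that any particular p-value would be reported.

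No primary or secondary conclusion depends on these endpoints, so this is a minor to moderate correction.

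**What to change.** In Protocol 15.5 and SAP 10.4, replace the rule for binary endpoints with wording such as: *For binary exploratory endpoints the arm difference will be estimated by Firth-penalised logistic regression with treatment, sex and age group and no interaction terms, with a profile-likelihood 95% CI and a penalised likelihood-ratio p-value, together with the risk difference and an exact 95% CI. Results by sex and age group will be shown as counts.* Exempt binary endpoints from the sentence that puts interactions in all models.

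Penalisation alone is not enough. At 6 v 0, Firth with the interactions kept gives a median p of 0.23, against 0.011 without them, because the coefficient still describes one stratum.

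The cost is a wording change and one procedure option. The downside is that subgroup effects on binary exploratory endpoints are tabulated and not modelled.
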